9.2 SAMPLE SIZE DETERMINATION

Screening and Clinical Assessment (SCA) Arm: We calculated the width of the exact 95% CI for detecting CASH cases, varying the prevalence from 10% to 25% based on the range in preliminary data, and total sample sizes screened from 500 to 1,500. Based on these sample size models, we propose recruiting 200 CASH cases for the SCA arm of this project, to be enrolled during years 2-5, an average of 50 cases/year at all sites, and less than one case/site/month. Assuming a 15% prevalence of CASH cases (the average in three ongoing registries), a screening sample size of 1,333 would be required over a 4-year period (333 cases to be screened/year) to detect 200 CASH cases \pm 2% (i.e., 13% to 17%). Even if the true prevalence is lower (e.g. 10%) or higher (25%), we will have excellent precision to within \pm 1.5% to 2.5%, respectively, corresponding to 134 - 334 CASH cases for the same screening sample size. These CASH sample sizes will also allow flexibility in describing the proportion of important subgroups (i.e. sex, lesion location, genotype), and provide realistic estimates of recruitment at SCA sites (screened/enrolled ratio).

The 7 main sites are all high-volume CA clinical centers, with demonstrated ability to screen the requisite number of cases. Their recent clinical activity is demonstrated by the number of CA cases (n) seen over a 12-month period with diagnosis ICD9 228.02 on initial or follow-up visits at each of the institutions: 1) University of Chicago (n=106), 2) Mayo Clinic-Rochester (n=70), 3) University of New Mexico (n=80), 4) University of Utah (n=40), and 5) Barrow Neurological Institute, Phoenix (n=200); TOTAL (n=496). We would need to screen 1,333 CA cases over a 4-year period at the 5 sites (333 CAs screened each year), in order to identify and enroll 200 CASH cases, based on the estimated prevalence of 15% CASH cases among overall CA cases. This is a very realistic target, with 496 CAs actually evaluated per year at the 5 sites for the SCA arm. To help meet the target enrollment, The University of California- San

Francisco (n=70) was added as a recruitment site in February 2019 and Johns Hopkins University (n=150) will be added in 2020. If we do not meet our target enrollment of CASH cases, we may add additional, yet to be decided on, sites.

Follow-up and Biomarker Validation (FUBV) Sites: University of Chicago, University of New Mexico, Mayo, University of California San Francisco, and Johns Hopkins were chosen because of additional established infrastructure for advanced imaging, including identified MRI physicists, neuroradiologists and site engineers who will work with the Biomarker Imaging Core (BIC) on implementing QSM and DCEQP protocols. A subset of approximately 120 CASH cases will be enrolled at FUBV sites to perform imaging biomarker validation studies (Specific Aim 2) and follow-up of CASH cases annually for up to two years (Specific Aim 3) to evaluate changes in outcomes. This subset of CASH cases will undergo a research MRI scan at baseline and at 1 and 2-year follow-up visits and undergo modified Rankin Scale (mRS) score and EQ-5D, PROMIS 29, and NIHSS assessments. A target recruitment of 120 CASH cases over 3-4 years at the sites conducting the FUBV arm is amply justified, with demonstrated 256 CA cases recently evaluated per year at those sites, expecting to identify 38 CASH cases each year (15% prevalence). Utah and Barrow may also serve as alternate FUBV arm sites if needed, with large demonstrated CA clinical activity. The University of California San Francisco and Johns Hopkins are now part of the FUBV arm.

Assuming a sample size of 120 CASH cases, and allowing 30% dropouts or missing biomarker or other data, we would have 84 evaluable patients (168 patient-years). We project 10%-20% re-bleed rate/year, supported by population studies and meta-analyses of CASH^{18, 19}, with the higher estimate particularly applying to brainstem cases. We would hence expect 17-34 SHs. Based on this, for continuous outcomes we will have 80% power at an alpha level of 0.05, to detect a difference between the means of patients with and without re-bleeding of at least 0.63-0.77 standard deviation. For categorical outcomes (i.e. presence or absence of a risk factor) we will be able to detect a difference of 32-40% between these two groups. This allows testing of questions regarding the rate of SH, and the prevalence of other outcomes in relation to SH during follow-up (Specific Aim 3).

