1 PROTOCOL SUMMARY

1.1 SYNOPSIS

Title:	Trial Readiness in Cavernous Angiomas with Symptomatic Hemorrhage
Study Description:	This U01 project will address gaps in knowledge and barriers to clinical trial readiness in cerebral cavernous angioma patients with recent symptomatic hemorrhage (CASH)
Objectives:	
Primary Objectives:
 
1. To assess enrollment rates, harmonize data and determine baseline characteristics of patients with CASH across sites2. MRI Biomarker Validations3. Rate of recurrent symptomatic hemorrhage over 2 years in patients with CASH. 
Secondary Objectives: Functional status of CASH cases at enrollment and during follow-up; impact of bleed on functional status

Endpoints:	
Primary Endpoint (Aim 3):
 
• Recurrent bleeding during follow-up, homogeneity in years 1 and 2 
Secondary Endpoints (Aim 3):
 
• Biomarker changes during follow-up, homogeneity in years 1 and 2• Functional status and quality of life change in years 1 and 2 compared to baseline
Study Population:	Adult patients with cerebral cavernous malformations (CCMs) who have had a symptomatic hemorrhage within the prior year, where the bleeding lesion has not been excised or radiated
Phase:	Trial readiness
Description of Sites/Facilities Enrolling Participants:	Seven high volume cavernous angioma clinical centers University of Chicago, Mayo Clinic, University of Utah, University of New Mexico, Barrow Neurological Institute and University of San Francisco and Johns Hopkins University. Additional sites may be added as needed to reach enrollment goals.
Description of Study Intervention:	This is an observational cohort study of CASH cases with no intervention.
Study Duration:	The study will last 5 years.
Participant Duration:	Patients enrolled in the Screening and Clinical Assessment (SCA) arm will have a single, baseline visit. Patients enrolled in the Follow-up and

Biomarker Validation (FUBV) arm will have a baseline visit, along with two yearly follow-up visits, for a total of 3 visits. This is an observational study and all study visits can be completed remotely via telephone and/or telemedicine platforms.

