Years 3-4	
Publish guidelines paper on reporting Terminology in CAs by the end of year 3.Screen at least 50 cases/year, enroll 10 CASH cases/year at each SCA/FUBV site.Log follow-up at least 40 cases/year for sites participating in the FUBV arm by the end of year 3 and 60 cases by the end of year 4 with clinical and biomarker data.Confirm quality and consistency of harmonized data acquisitions across sites at the end of years 3 and 4.Complete lagging enrollments and follow-ups.Test hypotheses regarding relative value/sensitivity of outcomes instruments.Apply for certification of 1 or more outcomes instruments by the FDA.Formulate trial hypotheses.	
Decision regarding certifiable outcomes based on interim and/or final analyses of trial readiness aims (SH alone, versus QOL and biomarkers); application to FDA.Decision regarding # of subjects (and # of sites) needed for clinical trials, including stratification and outcome parameters.Decisions regarding multi-site trial models per results of readiness aims. Pharma, StrokeNet and NCATS consultations.
Year 5 (6)		

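### Section 9.2's 84 evaluable patients, 168 patient-years and 0.63-0.77 SD do not fit 3-4-year FUBV accrual in a 5-year study; the two-group comparison of 24-month change has about 47-69% power, not 80%

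*Combined protocol and SAP*

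**What the plan says.** Section 9.2 takes 120 FUBV cases, allows 30% for dropout or missing data, and says "we would have 84 evaluable patients (168 patient-years"). It applies a re-bleed rate of 10-20% per year, expects 17-34 symptomatic hemorrhages (SH), and claims 80% power at alpha 0.05 "to detect a difference between the means of patients with and without re-bleeding of at least 0.63-0.77 standard deviation". For categorical outcomes it adds "we will be able to detect a difference of 32-40% between these two groups".

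On timing, the same section gives "A target recruitment of 120 CASH cases over 3-4 years at the sites conducting the FUBV arm", supported by "expecting to identify 38 CASH cases each year (15% prevalence"). Section 4.1 puts set-up and pilot cases in year 1 and enrolment in years 2-5. The synopsis says "The study will last 5 years". The last FUBV visit is at month 24 (sections 1.3 and 8). The milestone table in section 10.1.2 still has, for years 3-4, "Screen at least 50 cases/year, enroll 10 CASH cases/year at each SCA/FUBV site", and its last row is labelled year 5 with a 6 in parentheses.

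Sections 4.3 and 7.1 keep patients with a recurrent SH and an unresected lesion in follow-up. Section 9.1 (Aim 3) compares changes over 1- and 2-year epochs between patients with and without recurrent SH by a two-sample test.

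**The concern.** There are two problems, of unequal weight.

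- **Timetable (main).** The 168 patient-years are 84 x 2, so no evaluable patient is cut short by study close. With enrolment from year 2 over 3-4 years and a close at the end of year 5, anyone entering after the end of year 3 cannot complete month 24.
- **Events counted as patients (minor).** A patient can bleed more than once, so 17-34 events are not 17-34 patients with re-bleeding. If re-bleeders left follow-up instead, 168 patient-years would not be reached.

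The study exists to endorse or reject outcome instruments for later trials (section 3). A null 24-month comparison by re-bleed status, believed to have 80% power, could count against a biomarker or quality-of-life scale when the comparison was simply too small.

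**Working it through.** **Inputs.** 120 enrolled, 30% loss, 10-20% per year, two-sided alpha 0.05, 80% power, accrual over 3-4 years (9.1, 9.2); enrolment from the start of year 2 (4.1); close at the end of year 5 (1.1). Assumptions: even accrual, constant re-bleed rate, loss unrelated to entry date. Tests are two-sample t (noncentral t).

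**1. The plan's own figure.** 120 x 0.70 = 84; 84 x 2 = 168; 168 x 0.10 = 16.8 and 168 x 0.20 = 33.6. Groups of 17 v 67 give 0.770 SD and 34 v 50 give 0.630 SD. This matches 0.63-0.77, so event counts were used as group sizes.

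**2. Patients instead of events, full follow-up.** Patients with at least one SH = 84 x (1 - exp(-2r)) = 15.2 to 27.7, giving 0.80 to 0.66 SD and about 77% power at the stated differences. If 10-20% is an annual risk, 84 x (1 - (1 - r)^2) = 16.0 to 30.2, giving 0.79 to 0.64 SD and 78%.

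**3. Who can reach month 24.** Entry is needed by the end of year 3.
- 3-year accrual: 2/3 x 120 = 80. With the 1-month visit window, 25/36 x 120 = 83. With five year-1 pilot cases as well, 5 + 115 x 25/36 = 85.
- 4-year accrual: 2/4 x 120 = 60. With the window, 25/48 x 120 = 62.5. With five pilot cases as well, 5 + 115 x 25/48 = 65.

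Truncation alone therefore takes about 29-33% or 46-50%, against a 30% allowance for all causes.

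**4. After 30% loss.** 80 x 0.7 = 56 and 60 x 0.7 = 42. Two cross-checks:
- At 38 per year, 76 enter in years 2-3, and 76 x 0.7 = 53.
- At the milestone 10 per site per year, five FUBV sites enter 100 in years 2-3, and 100 x 0.7 = 70.

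**5. Two-group comparison of 24-month change**, re-bleeders = n x (1 - exp(-2r)):

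| Patients at month 24 | Re-bleeders | Detectable difference (SD) | Power at stated 0.77 / 0.63 SD |
|---|---|---|---|
| 70 (milestone rate, five sites) | 12.7-23.1 | 0.88-0.72 | 69% |
| 56 (3-year accrual) | 10.2-18.5 | 0.99-0.81 | 59% |
| 42 (4-year accrual) | 7.6-13.8 | 1.15-0.94 | 47% |
| 80 (3-year, no dropout) | 14.5-26.4 | 0.82-0.67 | 75% |
| 60 (4-year, no dropout) | 10.9-19.8 | 0.95-0.78 | 62% |

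Reading the rate as an annual risk raises power by 1-2 points.

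**6. Exposure of the 84.** Mean follow-up is 2/3 x 2 + 1/3 x 1.5 = 1.833 years (3-year accrual) or 1/2 x 2 + 1/2 x 1 = 1.5 years (4-year). Times 84, that is 154 or 126 patient-years, not 168. If the 36 dropouts give half their available time, total exposure for the SH rate is (84 + 18) x 1.833 = 187 or (84 + 18) x 1.5 = 153.

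**7. If a sixth year exists.** 3-year accrual restores 84 patients and 168 patient-years. Under 4-year accrual, 3/4 x 120 = 90 can reach month 24, 63 after loss, with 157.5 patient-years for the 84 and about 64% power.

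**The case against.** - **The plan may run into year 6.** The last milestone label hints at this, and the table foresees completing late enrolments and follow-ups. With 3-year accrual a sixth year removes the shortfall, so the documents do not show that 84 patients at month 24 is impossible. The synopsis still says five years, and 4-year accrual still falls short.
- **Accrual may be faster.** The 38 per year is 15% of 256, the total of three sites (106 + 70 + 80). Adding the two later FUBV sites (70 + 150) gives 476 x 0.15 = 71 per year, or 120 in 1.7 years if every identified case enrolled. But section 9.2 names five sites and still states 3-4 years, and two of them joined later. Having 84 at month 24 requires all 120 entered by the end of year 3.
- **The 30% covers any cause.** Late entry can be read as missing data. Under 3-year accrual, truncation alone then about uses up the allowance and leaves nothing for real attrition; under 4-year accrual it exceeds it.
- **Follow-up is described as lasting up to two years.** That permits shorter follow-up, but it does not fit 84 x 2.
- **Section 9.2 never names 24-month change.** True. It gives one figure for all continuous outcomes, and section 9.1 makes the two-group comparison of 2-year change one of them.
- **The midterm option of 6- and 18-month visits** would ease truncation, but gives up month 24.

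A reader might infer that the secondary endpoint "Functional status and quality of life change in years 1 and 2 compared to baseline", or the year 1 v year 2 homogeneity question, lacks its claimed power. The documents do not support that. The first is a within-patient comparison and the second is not a re-bleeder v non-re-bleeder test; neither rests on 0.63-0.77 SD. They lose precision at month 24, but no stated power claim for them fails.

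**Conclusion.** The point holds, with limited scope. On the stated timetable, section 9.2's exposure and detectable difference do not carry over to the two-group comparison of 24-month change. That comparison detects about 0.72-1.15 SD with 42-70 patients, and power at the stated differences is about 47-69%. Even with no dropout, power is about 75% (n = 80) or 62% (n = 60). These figures assume close at the end of year 5, even accrual (or the milestone rate for n = 70), a constant 10-20% per year and 30% loss on top of truncation.

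Counting events as patients is a genuine slip but small: 0.66-0.80 SD (0.64-0.79 under annual risks) instead of 0.63-0.77.

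It would be wrong to conclude that the primary Aim 3 endpoint is undermined. Kaplan-Meier and per-patient-year rates handle censoring, data before attrition are kept, and total exposure may be near or above 168 patient-years. Baseline risk-factor comparisons can use all 120; with exponential dropout of 30% by two years they detect about 0.59-0.74 SD (3-year accrual) or 0.62-0.80 SD (4-year), so the stated range is about met.

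**What to change.** In section 9.2:

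1. Reconcile the five-year duration in the synopsis with the milestone label that suggests a sixth year. State either that FUBV enrolment closes 24 months before data close, or that FUBV follow-up runs into year 6.
2. Base group sizes on patients with at least one SH: about 15-28 of 84, detectable difference 0.66-0.80 SD with complete follow-up. Recompute the 32-40% categorical figure on those sizes with the sponsor's own test and base proportion, which the section does not state.
3. If 3-4-year accrual with close at year 5 stays, give 126-154 patient-years for the 84, with dropouts' earlier time shown separately for the SH rate. Add a separate detectable difference for 24-month change, using the number expected to reach month 24 under the current site list and accrual rate, with assumptions stated (about 42-70 patients; 0.72-1.15 SD).

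The cost is a rewritten paragraph and less favourable stated figures. No extra patients are needed; a sixth year would extend follow-up only if the sponsor chooses it.

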9.3 POPULATIONS FOR ANALYSES

Cavernous angiomas with symptomatic hemorrhage (CASH) are most likely to re-bleed and cause further neurologic sequelae. It would be desirable to develop a drug that stabilizes CASH, and prevent recurrent bleeding. CASH with recent bleed, where surgical resection is not undertaken, are the most likely cases to be followed expectantly per current evidence based guidelines, with clinical equipoise for testing novel therapies to prevent re-bleeding. They are the most likely cases to be targeted for clinical trials.

Appropriate and complete statistical modeling of data collected by the sites for both SCA/FUBV arms are imperative to the planning, development, and completion of a successful Phase III interventional trial. The most critical component is the accurate assessment of the enrollment rates of CASH across several sites, as well as the between-site variability in these estimates. Both within and between sites variability will be used to adequately power a Phase III trial, will be calculated by developing random-effect models along with using appropriate link functions quantifying the rates of CASH in these models.

As a follow-up step, in-depth data analyses will be performed using the demographic, imaging, clinical and biomarker data collected. These are applied to develop models assessing how predictive each of these factors is to the development of recurrent SH. Understanding which factors are most predictive of SH will be crucial in developing a covariate adaptive randomization scheme for the Phase III trial that insures proper balance in these prognostic factors between treatment arms. Finally, statistical assessments of changes in lesional iron content and permeability biomarkers, QOL, mRS, and NIHSS during follow-up of CASH patients will be performed. Understanding how these measures change over time will be an important step in the process of developing hypotheses on the effect of treatment on these as putative secondary or surrogate outcomes, or as potential composite outcomes.

9.4 STATISTICAL ANALYSES

9.4.1 GENERAL APPROACH

Data collection. Key variables to be collected in this study will be decided on by all stakeholders in Year 1. At a minimum, these will include patient demographics, genotype, baseline MRI lesion features of the hemorrhagic CA (size, location), time from SH, prior bleeds/dates, and diagnosis date. Functional status will be measured using the modified Rankin Scale (mRS) score⁵⁷, Euro-QoL⁵³, PROMIS29⁵², and NIH Stroke Scale. PROMIS 29 short forms are an assessment of anxiety, depression, and fatigue, and have been validated for use in several common neurological disorders. Presence of obstructive sleep apnea. Recent findings suggest that sleep apnea results in decreased blood flow to the brain. This transient ischemia may be implicated in CA hemorrhage. Sleep apnea questions will be included in the dataset and response analyses as described under the topic Predictors of SH.

Data harmonization. Common data elements from each site will be reviewed, updated, and harmonized using an iterative, stepwise process based on DataSHaPER (DataSchema and Harmonization Platform for Epidemiologic Research) recommendations⁵⁸⁻⁶⁰. Questionnaires, codebooks, and protocols, etc. at the 3 established CA databases (Table 2) will be compiled and distributed for review. A series of Executive Committee teleconference calls will be held in Year 1 to decide on a set of 'target' data elements for potential clinical trials, as has been similarly done with the consensus process for developing clinical guidelines paper¹⁷. The EDHC and DCC will then develop standardized electronic data entry forms and codebooks for data collection. Each site shall be trained in abstracting and entering data for their cases online. Data will be collected prospectively in Years 2-5. Analysis datasets will be generated quarterly by the DCC for quality control analysis by EDHC.

Event Rate: Time to recurrent SH will be analyzed using Kaplan Meier method and Cox proportional hazards regression approach. Rates of recurrent SH/patient/year from initial SH qualifying event, and SH/patient/year from enrollment (potentially more relevant for trial modeling) will be estimated along with 95% CIs.

Biomarker changes over 2 years: Changes in mRS, EQ-5D, PROMIS 29, and NIHSS scores, mean lesional QSM and K_i during 1 and 2-year epochs will be compared using paired t-test or Wilcoxon signed rank test to assess changes within patients over time, including 95% CIs.

Predictors of SH: Two sample t-test or Wilcoxon rank sum test will be used to compare such changes between patients with and without recurrent SH. Categorical variables such as proportions of patients with a drop in mRS score ≥ 1 point, between patients with and without recurrent SH will be compared using Chi-square or Fisher's exact test. Associations of baseline characteristics (sex, lesion locations, familial/sporadic) and recurrent SH as a binary outcome (yes/no) will be assessed using univariable and multivariable logistic regression and reported as odds ratios and 95% CIs. Depending on the number of recurrent SH over the 2-year period, we may analyze re-bleeds as a continuous outcome and the associations of baseline features or biomarkers assessed using linear regression. Performance of final model(s) will be assessed using r^2 in the case of linear regression, area under the curve (AUC) and Hosmer Lemeshow goodness of-fit test⁵⁵ in the case of logistic regression, or concordance index in the case of Cox proportional hazards regression. AUCs between various models (univariable) will be compared using the method proposed by DeLong et al⁵⁶. For biomarkers, we will create a binary variable (yes/no) depending on whether the % change in mean lesional QSM or K_i during 1-year epochs exceed previously defined respective thresholds (+ 5.8% QSM and +39.6% for K_i) that were significantly associated with new clinical events at high sensitivity and specificity in previously stable lesions³³. We will then assess the association of this newly created variable ("biomarker event") with SH rate treated as both continuous (using two sample t-test or Wilcoxon rank sum test) and binary (using Chi-square or Fisher's exact test) outcomes of interest. Finally, we shall compare the sensitivity/specificity of changes in mRS, QOL, and NIHSS scores, and lesional QSM and K_i in relation to SH during the same epochs, using McNemar's test with SH (yes/no binary) as the reference standard. All tests will be two-sided and p-values <0.05 considered statistically significant.

We will calculate the proportion and exact 95% confidence interval (CI) of CASH cases among all CA cases at each SCA site and overall. Baseline characteristics will be summarized using chi-square tests for categorical variables and t-tests for continuous variables. Baseline Euro-QoL and PROMIS29 measures will be validated for use in CAs. Euro-QoL and PROMIS29 measures are scored on the T-score metric, with a mean of 50 and standard deviation (SD) of 10 in a referent population (mild, moderate, and severe impairment is defined as 0.5-1.0 SD, 1.0-2.0 SD, or 2.0+ worse than the mean, respectively). Spearman correlation coefficients will be calculated between mRS and Euro-QoL and PROMIS29 scales, and mean scores of Euro-QoL and PROMIS29 will be stratified by mRS levels. This analysis will allow us to determine ceiling effects of scores and how well the Euro-QoL and PROMIS29 data are distributed in CASH cases.

Homogeneity of event rates, biomarker changes, and other endpoints in years 1 and 2. This will be assessed, as it impacts (1) sample size calculations for time averaged assessments of the impact therapies, and (2) whether future trials should be conducted for 1 or 2 years.

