4.3 END OF STUDY DEFINITION

A participant is considered to have completed the study if he or she has completed all phases of the study including the last visit or the last scheduled procedure shown in the Schedule of Activities (SoA), Section 1.3.

Cases whose CASH lesion has been resected will be considered to have reached endpoint, and will not be followed further during the study. The indication for surgery shall be noted, including any SH prior to CASH lesion resection.

Cases who develop a recurrent SH during follow-up, and their CASH lesion has not been excised, will remain in the study until they complete follow- up, and will undergo all scheduled assessments.

If an enrolled subject decides to discontinue the study, fails follow-up, or develops an exclusion criterion after enrollment in the study (becomes pregnant, undergoes CASH lesion excision, etc.), he/she will be considered an attrition after recording the causative event. Data collected prior to the attrition shall still be included in the study and no further patient follow-up will take place. An allowance in sample size calculation is made for up to 30% attrition or missing data from any cause.

5 Study Population

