7 STUDY INTERVENTION DISCONTINUATION AND PARTICIPANT DISCONTINUATION/WITHDRAWAL

7.1 PARTICIPANT DISCONTINUATION/WITHDRAWAL FROM THE STUDY

Cases whose CASH lesion has been resected will be considered to have reached endpoint, and will not be followed further during the study. The indication for surgery shall be noted, including any SH prior to CASH lesion resection.

Cases who develop a recurrent SH during follow-up, and their CASH lesion has not been excised, will remain in the study until they complete follow-up. They will undergo the scheduled follow-up assessments at Years 1 and 2.

Participants are free to withdraw from participation in the study at any time upon request.

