Specific Aim 3. Time to recurrent SH will be analyzed using Kaplan Meier method and Cox proportional hazards regression approach. Rates of recurrent SH/patient/year from initial SH qualifying event, and SH/patient/year from enrollment (potentially more relevant for trial modeling) will be estimated along with 95% CIs. Changes in mean lesional QSM and K_i during 1 and 2-year epochs will be compared using paired t-test or Wilcoxon signed rank test to assess changes within patients over time, including 95% CIs. To test predictive, monitoring or surrogate outcome hypotheses, two sample t-test or Wilcoxon rank sum test will be used to compare such changes between patients with and without recurrent SH. Categorical variables such as proportions of patients with a drop in mRS score ≥ 1 point, difference in EQ-5D and PROMIS 29 scores, NIHSS scores, between patients with and without recurrent SH will be compared using Chi-square or Fisher's exact test. Associations of baseline characteristics (sex, lesion locations, familial/sporadic) and recurrent SH as a binary outcome (yes/no) will be assessed using

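### The 2-year changes in biomarkers, function and quality of life are tested with paired tests that drop anyone without a Year 2 visit, although up to 30% loss is planned and lesion resection ends follow-up

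*Combined protocol and SAP*

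**What the plan says.** Section 9.4.1 (Biomarker changes over 2 years) lists mRS, EQ-5D, PROMIS 29, NIHSS, mean lesional QSM and Ki, whose changes over one and two years "will be compared using paired t-test or Wilcoxon signed rank test to assess changes within patients over time, including 95% CIs". Section 9.1 (Specific Aim 3) gives the same tests for QSM and Ki. The same change scores then feed the comparison by re-bleed status: "two sample t-test or Wilcoxon rank sum test will be used to compare such changes between patients with and without recurrent SH".

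On missing data, Section 4.3 says: "An allowance in sample size calculation is made for up to 30% attrition or missing data from any cause". Section 9.2 turns this into numbers: "Assuming a sample size of 120 CASH cases, and allowing 30% dropouts or missing biomarker or other data, we would have 84 evaluable patients". For patients who leave, Section 4.3 adds: "Data collected prior to the attrition shall still be included in the study and no further patient follow-up will take place". It does not say how those data enter the Year 2 estimate.

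Section 7.1 sets two rules that decide who has a Year 2 visit. On resection: "Cases whose CASH lesion has been resected will be considered to have reached endpoint, and will not be followed further during the study". On re-bleeding without excision: "Cases who develop a recurrent SH during follow-up, and their CASH lesion has not been excised, will remain in the study until they complete follow-up".

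The plan gives no repeated-measures model, imputation or missing-data sensitivity analysis for these changes. The random-effect models in Section 9.3 concern rates of CASH across sites. Section 9.4.1 says that homogeneity of endpoints between years 1 and 2 will be assessed, without naming a method.

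**The concern.** Both the paired t-test and the signed rank test need two values per patient. For the baseline to Year 2 change, a patient seen at baseline and Year 1 but not at Year 2 contributes nothing. That is harmless for bias only if the patients who leave would have changed like those who stay.

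Three statements in the protocol make this doubtful. Section 2.2 says that lesions are typically excised only after significant clinical sequelae, usually one or more bleeds. Sections 4.3 and 7.1 stop follow-up at resection. Section 4.2 reports that QSM and Ki rose in lesions with an interval bleed or growth and did not change in stable lesions. Together they describe a plausible route by which patients with larger first-year changes lack Year 2 data.

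The Year 1 and Year 2 changes, and their homogeneity, are Aim 3 secondary endpoints (Section 1.1). Section 9.4.1 says that homogeneity bears on sample size and on whether future trials should last one or two years. With separate paired tests, a larger Year 1 sample is set against a possibly selected Year 2 sample.

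**Working it through.** **The plan's own figures (Section 9.2).**
- Evaluable patients: 120 × (1 − 0.30) = 84. Patient-years: 84 × 2 = 168. Expected bleeds: 168 × 0.10 = 16.8 and 168 × 0.20 = 33.6, stated as 17 to 34.
- Detectable difference (two-sample t-test, two-sided 0.05, 80% power): 0.77 SD for 17 against 67 patients and 0.63 SD for 34 against 50.

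All reproduce. The 30% is an allowance in the count and does not say how the missing values are analysed.

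**Who is left out.** At 30% loss, 120 − 84 = 36 patients are absent from the baseline to Year 2 test. If all leave after Year 1, 36 patients with Year 1 data add nothing to it. If half leave earlier, about 18 do. The 1-year test still has 120 or about 102 patients. A paired test at 80% power detects 0.309 SD with 84 patients, 0.280 SD with 102 and 0.258 SD with 120.

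**Assumptions for the bias.** The documents give no SD of change, correlation between visits or dropout mechanism. Assumed: SD of change 1 at both visits; true change 0.15 SD at Year 1 and 0.30 SD at Year 2; correlation ρ = 0.6 between the two changes; 120 patients; 30% total loss; early loss, if any, at random.

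The likelihood estimate of the Year 2 change is

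ȳ₂(seen at Year 2) + b × [ȳ₁(all with Year 1) − ȳ₁(seen at Year 2)],

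where b is the slope of Year 2 change on Year 1 change among patients with both. For dropout of this pattern it corresponds to a repeated-measures model.

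**Simulated 2-year change (truth 0.30 SD).**

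| Dropout after Year 1 | Timing of loss | Patients with Year 2 visit | All-visits estimate |
|---|---|---|---|
| Unrelated to change | either | 0.30 | 0.30 |
| Odds × 1.5 to 3 per SD of Year 1 change | all after Year 1 | 0.14 to 0.23 | 0.30 |
| Same | half before Year 1 | 0.20 to 0.26 | 0.30 |

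With ρ from 0.5 to 0.7 and odds × 2 to 3, the 95% CI from patients with a Year 2 visit covers the truth in 56 to 87% of runs if all loss follows Year 1, and in 80 to 91% if half is earlier. The all-visits estimate stays near 95%.

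**Precision when loss is random.** The variance is 1/84 = 0.01190 for the paired mean and ρ²/n₁ + (1 − ρ²)/84 for the all-visits estimate.
- n₁ = 120: 0.36/120 + 0.64/84 = 0.01062; ratio 1.12.
- n₁ = 102: 0.36/102 + 0.64/84 = 0.01115; ratio 1.07.

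So the gain is 7 to 12%.

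**Effect on the year 1 versus year 2 comparison.** The true second-year change here is 0.30 − 0.15 = 0.15 SD.
- Subtracting the two epoch estimates gives 0.14 − 0.15 = −0.01 at one end and 0.26 − 0.15 = 0.11 at the other, which looks like a plateau.
- A direct paired Year 1 to Year 2 test errs the other way. A Year 2 shift of 0.14 − 0.30 = −0.16 implies a Year 1 shift of −0.16/0.6 = −0.27 in the patients who stay. Their Year 1 mean is then 0.15 − 0.27 = −0.12, and the paired change is 0.14 + 0.12 = 0.26. At the other end: −0.04/0.6 = −0.07, Year 1 mean 0.08, paired change 0.18.

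The direction of the error therefore depends on how homogeneity is computed, which the plan leaves open.

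**When dropout depends on the unseen Year 2 change** (odds × 2 to 3 per SD, ρ 0.5 to 0.7, all loss after Year 1): patients with a Year 2 visit give 0.03 to 0.11, and the all-visits estimate gives 0.09 to 0.20, against 0.30. The model is less biased but still biased.

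**The case against.** The strongest reply is that the plan is less restrictive than it may look. It never limits the analysis to completers, it says that data collected before attrition stay in the study, and the 1-year tests use them. A reader might infer that Year 1 data are thrown away altogether. The documents do not support that: the loss is confined to contrasts that need Year 2.

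The mechanism is also only partly documented. Patients who re-bleed without excision stay in follow-up with all assessments. The 30% also covers pregnancy, withdrawal and missing scans, and scores can be collected remotely, so scores and MRI need not share one loss pattern. It would go too far to say that the changes are biased toward stability by a known amount. The dropout slope is assumed, and under random loss the bias is zero. This stands, and it limits the claim to a risk. It does not remove the risk, because resection remains an outcome-related exit.

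A third reply concerns the target. After excision there is no lesion on which to measure QSM or Ki, so an all-visits model estimates a value that could not have been observed. This stands too, and the plan should state the target openly.

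A reader might also ask for a site term because the biomarkers are not yet validated across sites. Aim 2 tests that directly, and a constant site offset cancels in a within-patient change, so a site main effect is no argument here.

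Finally, Section 10.1.4 foresees that statisticians will refine the plans in year 1. The current text nevertheless names a specific method.

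**Conclusion.** The point holds in limited form. For the 2-year and Year 1 to Year 2 changes, the named tests exclude every patient without a Year 2 visit, up to 36 of 120 under the plan's own allowance. One exit, resection, is plausibly related to the outcome, and no missing-data method is given. At 30% loss under the stated assumptions, the 2-year estimate falls from 0.30 SD to between 0.14 and 0.26 SD. It does not move if loss is unrelated to change, and the documents cannot say which case applies.

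Two further inferences are not supported: that the reported changes will certainly be too small, and that a likelihood model would restore the truth whatever drives dropout. The model is unbiased only if dropout depends on observed data. That is still a weaker requirement than the paired test has for the whole cohort. These are secondary endpoints, but they are meant to inform the length and size of later trials, so the change is worth making.

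**What to change.** - **Main analysis.** For QSM and Ki (each on a scale fixed in advance), EQ-5D and PROMIS 29, use a likelihood-based repeated-measures model over baseline, Year 1 and Year 2 with all available visits. Report the Year 1 change, the Year 2 change and their difference (the second-year change), each with a 95% CI, and base the homogeneity assessment on these.
- **Ordinal and bounded scores.** Use an ordinal repeated-measures model for mRS and a model suited to a bounded score for NIHSS.
- **Sensitivity analyses.** Keep the paired tests, and add one analysis that allows non-random dropout, for example by shifting the missing Year 2 values of leavers over a range fixed in advance.
- **Target and reporting.** State that for the lesional biomarkers the model estimates the change had the lesion not been resected. Tabulate reasons for loss by recurrent SH status.

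The cost is SAP wording and a little more analysis work. No new visits or data are needed. The main analysis would rest on missing at random, which should be stated.
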